
DATA COLLECTION & ANALYSES
	
Descriptive statistics will be performed using data collected from the health questionnaire and measures obtained from the medical testing. Demographic data of participants will be compared to 1996 Canadian census data to determine the extent in which the survey results can be generalized to the Port Colborne community. Response rates will be estimated across geographical regions of Port Colborne to evaluate the potential for response bias. Prevalence rates for selected health conditions will be summarized for the Port Colborne area, and where sample size permits, the rates will be compared across stratified sampling areas. Similarly, the occurrence of selected health conditions in Port Colborne will be compared to participants of the Canadian Community Health Survey, a recently conducted national health survey. Tests of significance, including confidence intervals will be presented for these comparisons. Multivariate methods will be used to adjust for differences in age and sex of the comparison populations.
 
Levels of the individual Chemicals of Concern, as determined by biological specimens analysis, will also be summarized. Variations in exposure levels within Port Colborne will be explored by calculating descriptive statistics, and through the use of multivariate analysis of variance methods. Logistic regression will be used to evaluate the relationship between the selected health conditions and exposure to Chemicals of Concern from both biological specimens and relevant questionnaire items of the health questionnaire. These models will provide odds ratios that will be adjusted for the effects of other potential confounding variables, such as age, sex, smoking habits, alcohol use and other indicators of socio-economic status. In addition, multivariate analysis of variance will be used to compare laboratory measures of Chemicals of Concern taken in Port Colborne residents to a normative sample, while adjusting for age and sex.

Abbreviations

ATSDR	Agency for Toxic Substances and Disease Registry
CBRA	Community-Based Risk Assessment
CCHS	Canadian Community Health Survey
CDC	Center for Disease Control
CHAP	Community Health Assessment Project
CO	Carbon Monoxide
COHb	Carboxyhaemoglobin
CoCs	Chemicals of Concern
CRF	Case Report Form
DLC	Differential Leukocyte Count
ECG	Electrocardiogram
ft4	Free Tetraiodothyronine (Thyroxine)
FEV1	Forced Expiratory Volume in 1 Second
FVC	Forced Vital Capacity
Hb	Haemoglobin

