3.2.1.2 Current medical health status

The questions under the Current Medical Health Status section of the questionnaire are designed to help determine the prevalence of specific health conditions. These questions will address a number of specific health areas that have been linked to CoCs exposure or that have been expressed as community concerns. These include health areas relating to respiratory, dermatologic, cardiovascular, thyroid, gastrointestinal, hepatic, neurological, and reproductive questions. These questions come primarily from the Canadian Community Health Survey (CCHS) an existing, validated questionnaire used by Statistics Canada to provide regular and timely cross-sectional estimates of health determinants, health status and health system utilization for 136 health regions across the country. Therefore, much of the data extracted from the Current Medical Health Status section of the questionnaire can be compared to existing data.

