4.2.2.1 Questionnaire development and internal testing

Questions from the demographic section of the questionnaire were derived from the CCHS. Most of the questions collecting exposure information were developed under the advisement of experts in the areas of toxicology and environmental health and safety.

Questions pertaining to the smoking of cigarettes and consumption of alcohol were borrowed from the CCHS. The questions that assess quality of life came directly from the HRQOL-4 questionnaire that was developed by the CDC. There are five symptom questions within the section of the questionnaire that collects information on current medical health status. These questions were used in the work done by Smith-Sivertsen and colleagues (2000). The rest of the health related questions come from the CCHS, with a few exceptions for health outcomes of particular interest for this study. Finally, all questions on drug use and mental health again come from the CCHS.

The only identifying information collected in this questionnaire is the individual's name and date of birth. This information will be entered into the data entry application and will only be used for identifying individuals if they request their data. Otherwise, all identifying information will be permanently removed before any analyses take place.

During the development of the health questionnaire, wording was not modified for the CCHS-derived health questions, the HRQOL-4 questions, or the questions borrowed from the research done by Smith-Sivertsen et al. (2000). These are pre-existing, validated questions that require consistent phrasing so as to allow for comparisons with other datasets.

Once the health questionnaire has been finalized, questionnaires will be prepared for pre-testing. This pre-testing will also allow for data entry, handling, and analyses procedures

to be checked, and thus they will need to be in place prior to the pre-testing. The questionnaire will be pre-tested while interviewer training proceeds.

During the pre-test, the interview team will duplicate as closely as possible the procedures that will take place during the administration/fielding of the final questionnaire. While the pre-test is being conducted, progress will be closely monitored, noting and addressing any problems that arise in terms of the content or administration of the questionnaire, or the data management and analyses process.

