6.2.1.1 Demographics

The demographic information collected will include: date of birth (from which age can be calculated), sex, race, height and weight (from which body mass index can be calculated), household size, marital status, education, and income. This information will be used to adjust the data if the sample distribution is different than that of the real or true distribution in the population. Thus, it is important in assessing whether a representative sample has been drawn. This data can also be used to adjust for differences when comparing to provincial or normative data.

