6.3.1 CCHS Data

The Canadian Community Health Survey is an instrument used by Statistics Canada to collect health data at both the health region and province/territory levels. The survey targets persons 12 years or older, living in private dwellings in 10 provinces and 3 territories. Exclusions include persons in institutions, persons living on Indian Reserves or Crown lands, full-time members of the Canadian Armed Forces and residents of remote regions. The CCHS takes a representative sample of approximately 98% of the Canadian population aged 12 and older (over 130,000 nationwide, approximately 30,000 in the province of Ontario). The data is currently available for the content of the September 2000 version, and comparisons will be made to that data for Ontario.

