6.4 Statistical Analysis

The frequency distributions of variables collected within the health questionnaire and medical tests will be tabulated. The number of missing responses for each variable will be presented, and where possible, these missing values will be treated as a separate category. Particular attention will be given to examining response rates for income levels, since this variable will be used as a proxy to socioeconomic status. If necessary, other factors, such as education, may need to be used instead.

Prevalence rates for health conditions will be calculated by age-group for males and females. Statistically significant differences across strata will be evaluated by using the Chi-Square and likelihood ratio tests for categorical data, and the Student's t-test for continuous data. Multivariate analysis of variance will be used to adjust comparisons for the influence of potential confounding variables. Comparisons will need to take into account possible differences in the age and sex structure of the populations being compared. Of particular interest will be the comparison of Area 3 (otherwise known as the Rodney Street area) to the rest of Port Colborne. Comparisons will also be made to reference data for Ontario or other normative data.

To evaluate the potential influence for response bias, where possible, socio-economic characteristics will be compared between non-respondents and participants. These variables will include: age, sex, family size, income level, and neighborhood of residence. Statistical tests of significance will be performed to determine whether non-responders differed from those who participated in the survey. Response bias will also be examined by comparing survey results obtained from the 1996 Canadian census data.

The prevalence of selected health characteristics will be compared to responses obtained from participants of the 2000 CCHS. In order to control for differences in the underlying populations, direct standardization will adjust for the age and gender make-up of the populations being compared. The ratio of these standardized rates will be calculated, and

95% confidence intervals of this ratio will be used to assess statistically significant differences.

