Lifestyle and Dietary Information of Participants, by Sampling Areas,
CHAP Comprehensive Health Questionnaire, Fall 2002

	Area 3	Areas 1, 2, 4, 5	Total for Port Colborne	p-value [†]
	N (%)	N (%)	N (%)	
Occupation related to Exposure *				
Yes				
No				
Primary Source of Drinking Water				
Municipal				
Well				
Bottled				
Gardening Activity				
Yes				
No				
Non-occupational Activities related to Exposure to CoCs **				
Yes				
No				
Cigarette smoking status				
Never				
Current				
Former				
Unknown				
Exposure to second-hand Smoke				
Never				
As a child only				
As an adult only				
As a child and adult				
Current alcohol consumption				
Less than once a month				
1 To 3 times a month				
4 to 12 times a month				
> 12 times a month				
Jewelry piercings				
Yes				
No				

* Includes the following occupations: mining; metal cutting, grinding and refining; smelting; foundry work; steel making; welding; plumbing; brazing; plumbing; shipbuilding; metal plating or electroplating; boiler maker/repairer

** Includes painting, renovations, landscaping and automotive work

† p-value is based on Chi-square for comparison of proportions.

Table 5.
Prevalence of Selected Health Conditions of Participants, by Sampling Areas,
CHAP Comprehensive Health Questionnaire, Fall 2002

	Area 3	Areas 1, 2, 4, 5	Total for Port Colborne	p-value [†]
	N (%)	N (%)	N (%)	
Chronic Bronchitis				
Emphysema / Chronic Obstructive Pulmonary Disease				
Other Allergies				
Asthma				
Hypertension				
Heart Disease				
Thyroid Condition				
Stomach / Intestinal Ulcers				
Gastroenteritis				
Peripheral Neuropathy				
Arthritis				
Parkinson's				

[†] p-value is based on Chi-square for comparison of rates from Area 3 to Areas 1, 2, 4, and 5 after adjustment for differences in the age and sex distribution of the two populations.

Table 6.
External Comparison of Selected Health Conditions of Participants, by Sampling Areas,
CHAP Comprehensive Health Questionnaire, Fall 2002

	Port Colborne	Ontario	p-value [†]
	Prevalence	Prevalence	
Chronic Bronchitis			
Emphysema / Chronic Obstructive Pulmonary Disease			
Food Allergies			
Other Allergies			
Asthma			
Dermatitis			
High Blood Pressure			
Heart Disease			
Anaemia			
Thyroid Condition			
Stomach / Intestinal Ulcers			
Gastroenteritis			
Jaundice			
Parkinson's Disease			
Peripheral Neuropathy			
Parkinson's			

[†] p-value is based on Chi-square statistic of rates after direct standardization by age and sex. .

Table 7.

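### The Port Colborne–Ontario disease comparison is specified with age and sex adjustment only, so a smoking or income difference can look like, or hide, a health excess

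*Protocol*

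**What the plan says.** Three places in the protocol specify the adjustment for the Ontario disease comparison, and they agree:

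- Synopsis, data collection and analyses: "Multivariate methods will be used to adjust for differences in age and sex of the comparison populations".
- Section 6.4: "direct standardization will adjust for the age and gender make-up of the populations being compared". The decision rule follows: "95% confidence intervals of this ratio will be used to assess statistically significant differences".
- Section 6.5.1, footnote to mock Table 6: "p-value is based on Chi-square statistic of rates after direct standardization by age and sex".

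Section 6.3.1 names the comparator: "comparisons will be made to that data for Ontario".

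Other sections set a wider standard or supply the data for one:

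- Section 3.3 plans unadjusted, minimally adjusted (age and sex) and fully adjusted estimates as a general scheme.
- Section 3.3.1 says socio-economic status will be controlled for, and section 3.3.6 names cigarette smoke as a potential confounder.
- Section 6.4 adjusts the internal exposure–disease odds ratios for age, sex, smoking, alcohol and socio-economic indicators.
- Section 4.2.2.1 gives the source of the items: "Questions pertaining to the smoking of cigarettes and consumption of alcohol were borrowed from the CCHS". It says the demographic items, which include education and household income, were derived from the same survey.
- Section 6.2.1.1 says of the demographic items: "This data can also be used to adjust for differences when comparing to provincial or normative data".

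**The concern.** Comparison with areas outside Port Colborne is a stated objective (section 2.0), and Table 6 is the mock table that reports it for disease. Its rows include chronic bronchitis, emphysema/COPD, asthma and heart disease, conditions for which the protocol itself regards smoking as important. Yet the comparison stops at what section 3.3 calls the minimally adjusted level.

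The study is motivated by metal contamination (section 1.0), so a significant ratio in this table is likely to be read against that background. If Port Colborne differs from Ontario in smoking or income, part or all of the ratio may come from that difference. The error can also run the other way: if Port Colborne smokes less, a real excess is diluted.

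**Working it through.** **Can the general statements rescue the specific one?** Section 3.3 says all its techniques will be used, but ties none to Ontario beyond describing direct age standardization. The multivariate sentence in section 6.4 stands in the paragraph on differences across sampling strata; the later CCHS paragraph names its own method, covariates and decision rule. Section 6.2.1.1 is permissive, names no analysis, and does not list smoking or alcohol. The specific text therefore governs: age and sex.

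**Size.** The protocol states no power, precision or effect figure for the Ontario comparison, so there is none to reproduce.

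Inputs from the protocol:
- about 30,000 Ontario respondents (6.3.1);
- 500 participants in the Rodney Street area and 500 elsewhere (6.1.1);
- 719 residents aged 12 or over in Area 3 out of 16,355 (Table 2 of 6.1.1);
- 5% prevalence, the figure used for asthma (6.1.1).

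Assumptions: smoking prevalence *a* in Port Colborne of 30–35% (section 6.1 uses 30%, but only as a hypothetical), *b* in Ontario of 20–25%, smoker relative risk RR of 3–4, and no true difference within smoking strata.

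*Step 1, spurious ratio.* R = [1 + a(RR − 1)] / [1 + b(RR − 1)].
- 30% v 25%, RR 3: 1.60/1.50 = 1.07
- 35% v 25%, RR 3: 1.70/1.50 = 1.13
- 35% v 20%, RR 4: 2.05/1.60 = 1.28
- equal smoking: 1.00
- 25% v 30%, RR 3: 1.50/1.60 = 0.94, so a true ratio of 1.07 would be cancelled

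*Step 2, effective sample.* Section 4.1 weights the sample back to the city. The weights are 719/500 = 1.438 and 15,636/500 = 31.272. Kish effective n = 16,355² / [500(1.438² + 31.272²)] = 267,486,025 / 490,003 ≈ 546.

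*Step 3, false-positive rate of the 95% interval.* With p₀ = 0.05 and p₁ = 0.05R, SE(ln R) = √[(1 − p₁)/(546p₁) + (1 − p₀)/(30,000p₀)], and the rate is 1 − Φ(1.96 − ln R/SE) + Φ(−1.96 − ln R/SE).

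| R | ln R | SE | ln R/SE | false-positive rate |
|---|---|---|---|---|
| 1.07 | 0.065 | 0.182 | 0.35 | about 7% |
| 1.13 | 0.125 | 0.176 | 0.71 | about 11% |
| 1.28 | 0.248 | 0.166 | 1.50 | about 32% |

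A pooled-variance test of the difference in proportions gives about 7%, 12% and 34%. Setting the variance at 5% prevalence in both groups gives about 6%, 10% and 26%. Treating the 1,000 as a simple random sample would give about 8%, 16% and 52% on the tabulated formula, which overstates the problem because it ignores the weighting. The bias in R itself does not depend on sample size.

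**The case against.** The strongest defence is that an age-sex standardized ratio answers a legitimate descriptive question: how the burden of disease compares with the province. The primary objective is to characterize health status, the exposure question is assigned to logistic models that do adjust for smoking, alcohol and socio-economic status, and section 3.4 says the cross-sectional design makes cause and effect hard to discern. Section 3.3 already contains the minimal-then-full scheme. This stands as a reason to keep the age-sex ratio. It does not explain why the fuller one is left out of the comparison where the protocol tests for significance against Ontario.

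Limits on feasibility also stand:
- Section 4.2.2.1 promises unmodified wording for the CCHS-derived health questions, not expressly for the smoking, alcohol and demographic items.
- Section 4.2.2 makes income, education, smoking and alcohol questions adult-specific, while the sample starts at age 12.
- Some Table 6 conditions (dermatitis, gastroenteritis, jaundice, peripheral neuropathy) carry no CCHS mark in Appendix 10.1.
- The protocol does not say whether record-level CCHS data will be held.

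A reader might infer three stronger things that the document does not support. First, that wider adjustment is contemplated nowhere: section 6.2.1.1 leaves room for education and income, though it commits to nothing. Second, that Table 6 is the only external comparison: sections 6.3.2 to 6.3.4 plan others from published and reference data. Third, that the whole province is the wrong comparator because the CCHS covers "health determinants, health status and health system utilization for 136 health regions across the country". Ontario is a valid reference; a regional comparator would be a preference and would be less precise.

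**Conclusion.** The point holds for the comparison as specified. Age and sex are the only adjustment factors named for the Ontario disease comparison in the synopsis, section 6.4 and Table 6. This falls short of the protocol's own confounding standard, although the items needed were taken from the same survey.

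The spurious ratio is 1.07 to 1.28, with a false-positive rate of about 7% to 33% instead of 5%. These figures rest on assumed smoking rates and risks, 5% prevalence and a 500/500 split; the upper end needs a 15-point smoking gap and a relative risk of 4. Income and education could add to the bias or offset it and are not in the arithmetic. A reader might infer that the comparison will show a false excess. The document does not support that: the direction is unknown, and smoking contributes nothing if it is equally common in both populations. This is a worthwhile improvement to a stated objective, not a reason to discard the age-sex comparison.

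**What to change.** In section 6.4 and mock Table 6:

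1. Keep the age-sex standardized ratio and label it the minimally adjusted result. State that it describes burden and is not adjusted for smoking or socio-economic status.
2. Add a fully adjusted ratio with smoking, alcohol, education and income, from a weighted model pooling Port Colborne and CCHS Ontario records. If only tabulations can be had, standardize by age, sex and smoking status.
3. Restrict the fuller analysis to adults aged 18 and over and to conditions asked in the CCHS, after checking that the wording of the outcome and adjustment items matches.
4. Make the synopsis agree.

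The cost is some extra analysis and slightly wider intervals. Ages 12–17 and conditions not asked in the CCHS would have no fuller adjustment, and the table should say so.

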3.2.2.5 Validation

The individual medical tests described above have been included both for their utility in measuring general health and health conditions associated with exposure to the CoCs, as well as for purposes of validation. That is, specific medical tests also can be used as objective measures to validate reported medical health information from the health

questionnaire that is subjective in nature (Moffat et al., 2000; Smith- Sivertsen et al., 2000).

Medical tests that will serve as validators in this study include:

- Bilirubin test: validates the jaundice question in the questionnaire,
- Plasma cotinine test: validates recent smoking history question in the questionnaire,
- Serum TSH and fT4 test: validates thyroid condition questions in untreated individuals,
- ECG test: validates history of heart attack question in the health questionnaire,
- CO breath test: validates recent smoking history question in the health questionnaire,
- FEV1/FVC/PEFR tests: help to validate chronic bronchitis, emphysema, chronic obstructive pulmonary disease, asthma and other respiratory questions from the health questionnaire, and
- Skin patch tests: validates contact dermatitis question from the health questionnaire.

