3.3.6 Cigarette Smoking

Exposure to cigarette smoke has long been recognized as a leading cause of adverse health effects on respiratory symptoms and diseases (Bartal, 2001). Not only can smoking cause lung disease, it can make the lungs more susceptible to the negative pulmonary effects of other agents. In addition to its pulmonary effects, exposure to cigarette smoke may have other health consequences, including various types of cancer, cardiovascular disease, suppression of the immune system, and reproductive disorders (Bartal, 2001; Tengs and Osgood, 2001; Sopori, 2002). Given the broad effects of tobacco on human health, exposure to cigarette smoke should be considered a potential health confounder.

There are several biomarkers available to assess cigarette smoke exposure. For example, carboxyhaemoglobin (COHb) is often increased in smokers and can be assessed by single breath carbon monoxide (CO) levels (Middleton and Morice, 2000). Additionally, nicotine, the active substance in cigarette smoke, is intensively metabolized in the liver

and oxidized into cotinine (Berny et al., 2002). The measurement of cotinine allows the differentiation between non-exposed and tobacco-exposed individuals. As such, both breath CO and plasma cotinine tests will be included as part of the medical test battery to gauge cigarette smoke exposure, and to validate self-reported smoking patterns.

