6.2.2.3 Non-specimen related tests and data points

This battery of medical tests and assessments will include cardiovascular, respiratory, dermatology and general measures. Cardiovascular measures will be obtained via ECG and blood pressure tests. ECG tests are designed to exclude abnormal results across a number of different parameters and will include: sinus rhythm, QRS axis, P waves, PR interval, QRS complex, QT interval, ST segment, T wave and U wave. Blood pressure will also be assessed and abnormal results will be summarized in terms of frequency counts. Respiratory measures will include a breath CO test and a lung function test. Breath CO concentrations will be expressed in terms of whether they are above or below a smoking abstinence threshold value (this will be further validated using a cotinine plasma test). Outcome measures from the lung function test will include FEV1, FVC, and PEF. Finally, general measures will include height and weight to determine body

mass index that will aid in interpreting test results. Both means and frequency values will be used to represent these data.

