The logistic regression model will provide a parameter estimate that can be readily transformed into an odds ratio. This odds ratio provides a measure of risk that can be used to determine whether those with high levels of exposure to CoCs are more likely to have a specified health condition. Survey participants will be categorized into tertiles based on their clinical exposure measurements and into binary groups based on the answers they give to the exposure question in the health questionnaire. Risk estimates will be calculated by comparing the prevalence of disease among those in the highest tertile of exposure to those in the lowest and for those indicating exposure in their answers to the questionnaire versus no exposure. The 95% confidence intervals for these odds ratios will also be calculated. This confidence interval can be used to determine whether or not the association may be due to chance. These estimates of risk will be adjusted for the potential confounding influence of other relevant variables, such as age, sex, smoking habits, alcohol use, and indicators of socio-economic status. All statistical analyses will be conducted by using SAS. The fit of the model will be assessed by using the Hosmer-Lemeshow goodness of fit statistic.

Multivariate analysis of variance will be used to compare laboratory measures of CoCs taken in Port Colborne residents to a normative sample. These multivariate models will be adjusted by age and sex of the subjects. Differences between the two populations will be evaluated by using the F-test statistics generated from the ANOVA model. Where necessary, measured levels of CoCs will be transformed in order to ensure that assumptions of normality are satisfied. If this assumption cannot be met through a

transformation, than non-parametric methods (e.g., Wilcoxon Rank Sum test) will be considered.

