Comparison of the Mean Levels of Selected Biological Measures, by Sampling Areas,
CHAP Comprehensive Health Questionnaire, Fall 2002

	Area 3	Areas 1, 2, 4, 5	Total for Port Colborne	p-value [†]
	Mean (s.d)*	Mean (s.d)	Mean (s.d)*	
Haemoglobin				
White Blood Cell Count				
Red Blood Cell Count				
Haematocrit				
Mean Cell Volume of Red Cells				
Mean Hemoglobin Concentration of Red Cells				
Platelet Count				
Red Cell Distribution Width				
Mean Platelet Volume				
Differential Leukocyte Count				
Bilirubin				
Creatinine				
Plasma Cotinine				
Plasma Screen for Concentration of TSH				
Blood Urea Nitrogen				

[†] p-value is based on an ANOVA for comparing the means between Area 3, and Areas 1, 2, 4, and 5; after adjusting for difference in the age and sex distribution of the two populations.

* s.d. = standard deviation

Table 8.
Comparison of the Non-Specimen Tests Among Participants, by Sampling Areas,
CHAP Comprehensive Health Questionnaire, Fall 2002

	Area 3	Areas 1, 2, 4, 5	Total for Port Colborne	p-value [†]
	Mean (s.d) [*]	Mean (s.d)	Mean (s.d.)	
Calculated BMI				
Electrocardiogram	---	---	---	---
Blood Pressure				
Carbon Monoxide Breath Test				
Forced Expiratory Volume in 1 second				
Forced Vital Capacity				
Peak Expiratory Flow Rate				
Dermatology Patch: Nickel Sulfate				
Dermatology Patch: Cobalt Dichloride				

[†] p-value is based on an ANOVA for comparing the means between Area 3, and Areas 1, 2, 4, and 5; after adjusting for difference in the age and sex distribution of the two populations.

^{*} s.d. = standard deviation

Table 9.
Comparison of the Selected Measures of Chemicals Among Participants, by Sampling Areas, CHAP Comprehensive Health Questionnaire, Fall 2002

	Area 3	Areas 1, 2, 4, 5	Total for Port Colborne	p-value [†]
Chemical	Mean (s.d) [*]	Mean (s.d)	Mean (s.d)	
Nickel (Urine)				
Copper (Urine)				
Cobalt (Urine)				
Arsenic (Urine)				
Mercury (Urine)				
Lead (Blood)				

[†] p-value is based on an ANOVA for comparing the means between Area 3, and Areas 1, 2, 4, and 5; after adjusting for difference in the age and sex distribution of the two populations.

^{*} s.d. = standard deviation

Table 10.
Comparison of the Proportion of Tests Outside Normal Range for Selected Biological Measures,
by Sampling Areas,
CHAP Comprehensive Health Questionnaire, Fall 2002

	Area 3	Areas 1, 2, 4, 5	Total for Port Colborne	p-value [†]
Proportion Outside Normal Range				
Haemoglobin (normal range)				

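### Cigarette smoke is a named confounder with two biomarkers collected for it, but Section 6.4 gives neither a role in the smoking adjustment, and Table 10 would score non-smokers as abnormal on cotinine

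*Protocol*

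**What the plan says.** Section 3.3.6, within the confounders chapter, concludes that "exposure to cigarette smoke should be considered a potential health confounder". It then states that "both breath CO and plasma cotinine tests will be included as part of the medical test battery to gauge cigarette smoke exposure"; the same sentence adds validation of self-reported smoking as a second purpose.

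The uses spelled out elsewhere are narrower:

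- Section 3.2.2.5 lists both markers as validators: "Plasma cotinine test: validates recent smoking history question in the questionnaire" and "CO breath test: validates recent smoking history question in the health questionnaire".
- Section 6.2.2.3 reports breath CO as above or below an abstinence threshold and adds that "this will be further validated using a cotinine plasma test".
- Section 6.2.2.1 lists cotinine among the biochemistry outcome measures, to be reported as means and as counts within the reference range. Mock Tables 7 and 10 carry a "Plasma Cotinine" row compared between Area 3 and the other areas. Tables 8 and 11 do the same for breath CO.

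For the exposure odds ratios, Section 6.4 adjusts for confounders "such as age, sex, smoking habits, alcohol use, and indicators of socio-economic status". Section 3.3.2 describes smoking status as lifestyle information to be collected, and Section 4.2.2.1 takes the smoking questions from the Canadian Community Health Survey. Section 4.2.2 describes smoking status as an adult-specific item, but Questions 18 to 29 in Appendix 10.1 carry no adult tag. Appendix 10.4 gives one cotinine range, 20-700 ng/ml in smokers.

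**The concern.** Smoking bears on the respiratory and cardiovascular conditions under study. If some smokers report that they do not smoke, adjustment for reported status removes only part of the smoking effect. The rest is read as an effect of area or metal exposure. The study collects markers that could correct much of this for current smoking, but the analysis section does not say how they enter the models or what a failed validation changes.

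The gap stands out because Section 6.4 does handle two instruments for the metals: it runs models on both the specimen and the questionnaire measures and examines their concordance. Smoking is also measured by both routes and has no such rule.

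Two further points follow. If Section 4.2.2 is followed, participants aged 12-17 have no reported smoking to adjust for. And a cotinine row scored against a range that describes smokers cannot be read as a proportion outside normal.

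**Working it through.** **Size of the residual bias.** The protocol gives no smoking rates, denial rates or smoking effect, so every input here is an assumption. The true exposure odds ratio is set to 1, so any departure from 1 is bias.

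*Set A, Area 3 versus the rest.* Inputs: smoking 40% v 25%; smoking-disease odds ratio 3; prevalence in non-smokers 4%; groups of equal size; no non-smoker reports smoking.

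1. Odds in smokers = 3 × 0.04/0.96 = 0.125, so prevalence = 0.125/1.125 = 0.1111.
2. Area 3 prevalence = 0.40 × 0.1111 + 0.60 × 0.04 = 0.0684. Elsewhere = 0.25 × 0.1111 + 0.75 × 0.04 = 0.0578.
3. Crude odds ratio = (0.0684/0.9316)/(0.0578/0.9422) = 1.198.
4. Move the denying smokers into the reported non-smoker stratum and pool with Mantel-Haenszel: OR = Σ(a·d/T)/Σ(b·c/T), where a and b are cases and non-cases in Area 3, c and d the same elsewhere, and T the stratum total.

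With 20% denial in both areas, each area scaled to 1:

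| Reported stratum | a | b | c | d | T | ad/T | bc/T |
|---|---|---|---|---|---|---|---|
| Non-smoker | 0.03289 | 0.64711 | 0.03556 | 0.76444 | 1.48 | 0.01699 | 0.01555 |
| Smoker | 0.03556 | 0.28444 | 0.02222 | 0.17778 | 0.52 | 0.01216 | 0.01216 |

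OR = 0.02914/0.02770 = 1.052. The same steps give:

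| Denial, Area 3 / elsewhere | Adjusted OR | Share of crude excess (0.198) removed |
|---|---|---|
| 0% / 0% | 1.000 | 100% |
| 5% / 5% | 1.014 | 93% |
| 10% / 10% | 1.027 | 86% |
| 20% / 20% | 1.052 | 74% |
| 20% / 5% | 1.094 | 53% |

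*Set B, top versus bottom exposure tertile.* Inputs: smoking 40% v 20%; smoking odds ratio 3; prevalence in non-smokers 5%; specificity of reported smoking 98%. Crude 1.28; adjusted 1.04, 1.05 and 1.09 at sensitivity 95%, 90% and 80%.

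*Range.* Smoking contrasts from 35/25% to 50/10%, smoking odds ratios of 2 to 4 and sensitivity of 80 to 95% give residuals from 1.01 to 1.30. The top value needs 50% v 10% smoking, an odds ratio of 4 and 80% sensitivity together.

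**Cotinine in Table 10.** Section 6.2.2.1 calls for within-range counts, and Section 6.3.4 takes laboratory ranges from the appendices. Applying 20-700 ng/ml:

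- a non-smoker with cotinine below 20 counts as outside normal;
- a smoker at, say, 200 counts as normal.

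The row would run opposite to its heading, and an area with fewer smokers would appear to have more abnormal results.

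**Ages 12-17.** Section 4.2.2 restricts smoking status to adults. Question 30 on alcohol carries an adult tag in Appendix 10.1, but Questions 18 to 29 on smoking do not. The two places disagree, and the choice decides whether adolescents have any reported smoking data.

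**The case against.** The strongest reply is that the protocol never limits the adjustment to self-report. The list in Section 6.4 is open and names no data source, Section 3.3.6 includes gauging smoke exposure as a purpose of the markers, and Section 3.3 admits prespecified confounders by a 10% change rule. Marker-based adjustment is therefore permitted, and covariate coding is often left to an analysis plan. This stands in part: a reader might infer that the protocol fixes adjustment on reported smoking alone, but it does not say so. The questionnaire item is the natural reading, not a stated commitment. What remains is that the protocol assigns the markers specific roles, validation and between-area comparison, and attaches no analytic consequence to either.

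The size is also a fair objection. The residuals of 1.01 to 1.09 lie below the 10% change criterion and far below the detectable odds ratio of 2.1 for asthma in Section 6.1.1. Nothing in the documents suggests that denial differs by area.

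A reader might also infer that second-hand smoke goes unadjusted. The documents do not support that: it is collected (Questions 18 and 28), tabulated in Table 4, and not excluded by the open list. Nor can both markers be assumed available for everyone, because mock Table 1 counts refusals of biological testing.

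Finally, cotinine as a main covariate is debatable. The conditions are long-standing, Section 3.2.2.5 ties both markers to recent smoking, and someone who quit after diagnosis would have low cotinine because of the disease. Cotinine also marks nicotine from any source. This objection stands and shapes the fix.

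Showing cotinine by area is reasonable in itself. The fault lies in its label and in the range applied.

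**Conclusion.** The point holds in a limited form. The protocol names smoke exposure as a confounder and collects two markers to gauge it, but its analysis section gives them no part in the adjustment. Misreported smoking can then leave a modest bias in the exposure odds ratios, about 1.01 to 1.09 in the main scenarios, after adjustment for reported smoking has removed roughly half to nine-tenths of the confounding. These figures rest wholly on assumed smoking rates, denial rates and smoking effect. They show plausible size and are not an estimate for Port Colborne.

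It would go too far to conclude that the markers could remove smoking confounding altogether. They record recent exposure, and past smoking still has to come from reported history.

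The Table 10 problem needs no assumption about size: with the range given, the cotinine row is scored the wrong way round. The conflict over smoking questions for ages 12-17 is likewise plain from the text.

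**What to change.** - **Section 6.4, main models.** Define the smoking covariate from reported history (never, former, current, and amount). Classify self-reported non-smokers with cotinine in the laboratory's smoker range, 20 ng/ml or above, as current smokers. Keep reported status where biological testing was refused.
- **Section 6.4, sensitivity analysis.** Use cotinine as a continuous covariate only here, with a stated rule for non-detectable values.
- **Ages 12-17.** Reconcile Section 4.2.2 with the untagged Questions 18 to 29. If the adult-only restriction stands, state that the markers supply the smoking data for this group.
- **Tables 7 and 10.** Label cotinine as a smoke-exposure measure. In Table 10, replace the proportion outside normal range with the proportion in the smoker range.

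The cost is a few sentences in Section 6.4, one reconciliation and two table labels, with no new data. The downside is that cotinine reflects recent nicotine exposure from any source, so some recoded participants may not be cigarette smokers, and past smoking still depends on what participants report.
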